11.3.1 AE Descriptions and Reporting

AEs and SAEs will be documented when reported or noted in the participant's medical records by the treating team.

11.3.2 Intensity

The severity of each AE, including laboratory and testing abnormalities and results, will be graded according to Common Terminology Criteria for Adverse Events (CTCAE).

11.4 Reporting and Evaluation of SAEs

11.4.1 SAEs

The Site PI will review relevant records provided by the research team such as medical notes, laboratory results, and radiographic data. This information, along with the Site PI's assessment and diagnosis, will be recorded in the electronic Case Report Form (eCRF).

12. STATISTICAL CONSIDERATIONS

12.1 Rationale

Instead of evaluating safety and efficacy separately, we will apply an approach that is increasingly used in trials comparing therapeutic interventions for selected infectious diseases to provide a global evaluation of the benefits and risks of the intervention: Desirability of Outcome Ranking (DOOR), which can further be combined with antibiotic use outcomes, Response Adjusted for Duration of Antibiotic Risk (RADAR) ^{55–59}. In this approach, trial participants are ranked with respect to the desirability of their overall outcome, and during study analysis, the distribution of DOORs are compared between study arms. These are further analyzed with antibiotic use outcomes under the principle that less antibiotic use is better, but not at the expense of clinical outcomes. All participants will have a DOOR assigned based on a review of the individual patient during the course of the study, where the ranking will be constructed from a defined number of mutually exclusive hierarchical levels ranging from least desirable (death) to most desirable (e.g., cure, no adverse events). Using such a combined endpoint will

enable us to determine if BV-supported antibiotic treatment recommendation will yield better outcomes than usual care alone.

12.2 Definitions for clinical outcomes and ranking of outcome categories (DOOR)

Points are assigned for overall outcomes, with pre-specified definitions for treatment failure, complications and adverse events related to antibiotic use. All clinical outcomes will be reviewed by a 3-member clinical review panel, and all AE will be reviewed by a different 3-member panel (the Data Safety and Monitoring Committee). The panels will consist of experienced ID, Pharmacy and ICU experts (to be named) blinded to intervention and patient identity.

Clinical outcome	Definition
Treatment failure	Signs and symptoms of initial event (infectious illness) within 72h of end of antibiotic treatment
Infection persistence	Continued presence of signs and symptoms and of original causative pathogen at end of antibiotic treatment
Infection recurrence	New infection due to at least one of the original causative agents found at baseline (initial event)
Infectious complication	Signs and symptoms requiring surgical or other procedure in organ involved in initial event (eg. empyema post pneumonia) occurring >72h after end of antibiotic treatment

We will determine how many DOOR events (AE, infection recurrence etc.) occurred for each participant, then assign a mutually exclusive rank.

RANK	Criteria
1	Survival, clinical benefit of treatment, with NONE of treatment failure, persistence, recurrence, complication AND NONE of Grade IV adverse event (AE)
2	Survival, clinical benefit of treatment, with NONE of treatment failure, persistence, recurrence, complication, AND at least one of AE
3	Survival, at least one of treatment failure, persistence, recurrence, complication, AND NONE of AE
4	Survival, at least one of treatment failure, persistence, recurrence, complication AND at least one AE
5	Death

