12.7 Primary Analysis

The primary analysis will be an intent-to-treat (ITT) and will include 2 interim analyses at 1/3 and 2/3 enrolment. The final analysis will use Lan-DeMets stopping rules⁶². We will also perform per-protocol analyses where the treatment recommendations were followed.

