12.8 Frequency of Analyses

Our approach for interim monitoring is to test H1 first (null H1: no difference between intervention and control in terms of antibiotic exposure). Should the null H1 be rejected at the first interim, then the second hypothesis (H2: no significant difference in combined endpoint of adverse events between the 2 groups) will be assessed and decision to continue will be based on H2. If H1 is not rejected at the interim, then H2 will not be assessed until the final analysis. We estimate that H1 testing may cross the pre-specified boundary at one of the interim analyses, but H2 testing may only meet non-inferiority once full sample size is enrolled.

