13.1 Data Monitoring and Auditing

Data monitoring will be performed by data monitoring study team member based at the central (Glen) site, for completeness and plausibility, logic checks for accuracy, and will send queries to the study nurses in cases of ambiguity or errors. Data documentation will be performed continuously. Data verification for primary outcomes will be a priority.

The study coordinator may perform on-site monitoring of documentation by comparing data entry with source documents (eg. participant records) for completeness and chronology, logic checks for accuracy and trend analysis to identify problem areas. The site PIs will cooperate in resolving any queries or findings made during the monitoring process.

The Data safety and monitoring board (DSMB) will provide independent monitoring of interim results and make recommendations for continuation, modification or termination of the study. The DMSB will meet at two planned interim analyses for safety, at completion, and at any other needed interval.

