13.2 Data Safety and Monitoring Committee (DSMC)

This committee will be composed of at least 3 members, with at least one expert for each of infectious diseases, ICU, and pharmacy. The committee will be independent from the steering committee, and will initially define all the event triggers that would prompt unscheduled review, as well as review of interim and cumulative data for evidence of efficacy and safety. They will review data quality and completeness, factors that might compromise data confidentiality or affect outcomes. They will conclude each review with recommendation to the steering committee whether the study should continue without change, be modified, or terminated.

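### The DSMC is both the blinded adjudicator of adverse events and the reviewer of interim between-arm results, with no firewall stated, so blinding of AE adjudication is not assured from the first interim look

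*Protocol*

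**What the plan says.** **Adjudication.** Protocol Section 12.2 sets up two three-member panels. One reviews clinical outcomes. For adverse events, "all AE will be reviewed by a different 3-member panel (the Data Safety and Monitoring Committee". The panels draw on infectious-disease, pharmacy and ICU expertise, their members are still to be named, and they are to be "blinded to intervention and patient identity". No time limit or exception is attached to that blinding.

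**Monitoring.** Section 13.2 says of the DSMC: "This committee will be composed of at least 3 members, with at least one expert for each of infectious diseases, ICU, and pharmacy". Its tasks include "review of interim and cumulative data for evidence of efficacy and safety", and each review ends in a recommendation to continue, modify or terminate. Section 13.1 describes a board that "will provide independent monitoring of interim results and make recommendations for continuation, modification or termination of the study". It calls this body a DSMB, apparently the same committee under another name.

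**Interim looks.** Section 12.7 says the primary analysis "will include 2 interim analyses at 1/3 and 2/3 enrolment". Under Section 12.8, H1 (antibiotic exposure, intervention against control) is tested first. If it is rejected at the first interim, H2 (the combined adverse-event endpoint) is assessed and the "decision to continue will be based on H2".

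**The concern.** One committee is told to classify events without knowing the intervention and also to weigh interim results that compare the interventions. The two instructions pull against each other. A DSMC kept wholly blind to intervention is poorly placed to judge harm by arm. A DSMC that sees results by arm then classifies later AEs knowing the interim trend.

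The classification matters to the main results. In the Section 12.2 ranking, AE status is what separates rank 1 from rank 2 and rank 3 from rank 4. AEs are also part of what H2 compares. Several definitions in Section 11.3 call for attribution: the nausea and anaphylaxis rows require that nothing else explains the event, and the renal and neurologic rows require that it is not due to sepsis or the infectious syndrome. The study and treating teams learn the assignment when the intervention starts (Section 7.3), so blinded adjudication is one of the main protections against biased outcome classification.

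**Working it through.** The point concerns roles, so the main check is to set the sections side by side. The arithmetic only sizes the exposure.

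**1. Is it the same body?** Section 12.2 names the DSMC as the AE panel. Section 13.2 gives the DSMC interim efficacy and safety review. The conflict therefore holds on these two sections alone, even if the DSMB of Section 13.1 were a separate board.

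**2. Could different members fill the two roles?** The stated minimum in Section 13.2 is three members, one each from infectious diseases, ICU and pharmacy. That matches the AE panel in size and expertise. At that minimum, nobody on the committee is free of both roles. A larger committee could be split, but no split is described.

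**3. Is a safeguard stated?** The protocol mentions no firewall, adjudication subgroup or closed report. It does not say whether interim reports are pooled, coded or by named arm.

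**4. Would coded arms be enough?** H1 is one-sided, towards less antibiotic use (Sections 12.4 and 12.9). Once it is rejected, the code with lower use is the intervention. Coded labels then protect little at group level. An individual's allocation would still not be known from aggregate results.

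**5. Other routes to unblinding.** Recommendations are placed in the medical chart, and the BV value is available only for the intervention group (Section 8.5), so unmasked case files could reveal the arm. Serious, unexpected and related events go to the DSMB within 48 hours (Section 14.4), at any time and not only at the looks.

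**6. Exposure.** Inputs are N = 1200 (Section 4.1), a first look at 1/3 of enrolment (Section 12.7), and a Grade IV antibiotic-related AE rate of 5-10% excluding renal events (Section 12.6).
- First look: 1200 × 1/3 = 400 participants.
- Enrolled afterwards: 1200 − 400 = 800, or 2/3.
- With a Grade IV AE among these: 800 × 0.05 = 40 to 800 × 0.10 = 80.
- On the 1060 total of Section 12.4, 1060 × 2/3 ≈ 707, the same fraction.

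**7. Illustration of size.** Assume that 1 in 5 post-look AEs is reclassified, in one arm only. Neither assumption comes from the documents.
- Shift in that arm's composite rate = AE rate × 0.2 × 2/3.
- Low: 0.05 × 0.2 × 2/3 = 0.0067, about 0.7 points.
- High: 0.10 × 0.2 × 2/3 = 0.0133, about 1.3 points.
- Against the 4-point margin: 0.67/4 ≈ 1/6 to 1.33/4 ≈ 1/3.

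These are upper bounds under the assumption. Reclassifying an AE in someone who died or had another composite event does not change that person's H2 status.

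**The case against.** A reader might infer that AE adjudication cannot stay blinded once the DSMC has met. The text does not support that. An arm-level summary does not tell a member which arm a masked case file belongs to, and nothing says the committee receives allocation listings. A reader might also take it as given that members see results by arm. The protocol describes between-group tests but not who runs them or how they are reported. With coded reports and masked files the sections could coexist, and such details commonly sit in a charter that is not at hand. This part of the objection stands, and it is why the conclusion is that blinding is not assured.

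It does not dispose of the point. The protocol itself assigns both roles to one committee, and that wording would remain whatever a charter added.

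Three further objections have weight.
- Bias confined to one arm needs some knowledge of individual allocation, which is not shown. A shift in criteria without that knowledge would fall on both arms.
- Many Section 11.3 rows start from numeric thresholds, and severity is graded by CTCAE (Section 11.3.2). That narrows the room for discretion, although most of those rows keep exclusion clauses that need judgement.
- H2 is not tested at an interim where H1 is not rejected (Section 12.8). That limits the formal safety comparison the DSMC would see, but its remit in Section 13.2 still covers interim safety data.

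**Conclusion.** The point holds as a conflict of roles. Section 12.2 requires blinded AE adjudication by the DSMC, while Sections 12.8, 13.1 and 13.2 have it act on interim between-arm results, with no stated separation. Blinding of a component of the DOOR ranks and of H2 is therefore not assured from the first interim look. It is not shown to be lost.

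The exposure is two thirds of enrolment: about 800 participants, with about 40 to 80 Grade IV AEs. This rests on the protocol's 5-10% rate, which leaves out renal events, and on looks at the planned fractions of 1200.

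The documents do not give the size of any bias. The 0.7 to 1.3 points depend on an assumed 1-in-5 reclassification in one arm and are a ceiling under that assumption. A reader might apply the 1 in 5 to all AEs and arrive at 1 to 2 points, a quarter to a half of the margin. That would wrongly count the third of participants enrolled before the first look.

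**What to change.** Reword Section 12.2 so that AEs are adjudicated from masked case files by the existing blinded clinical review panel, which has the same infectious-disease, pharmacy and ICU expertise. State that no DSMC member who sees by-arm data adjudicates AEs. Limit the DSMC in Sections 13.1 and 13.2 to monitoring, and use one name for it throughout. This should be settled before the first interim look.

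The design, sample size and data collection do not change, and the members are still to be named. There are two costs: more case review for the clinical panel, and the loss of the present arrangement in which separate panels judge AEs and clinical outcomes. If that separation is valued, three experts from outside the DSMC could form the AE panel, at the price of one more group to convene.

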11.1 Definitions

11.1.1 Adverse Event (AE)

An AE is any untoward medical occurrence in a participant or clinical investigation participant, administered a study medication/intervention (e.g., recommendation for antibiotic cessation), which does not necessarily have a causal relationship with this treatment. An AE can therefore be any unfavorable and unintended sign (including an abnormal laboratory finding), symptom, or disease temporally associated with the use of a medicinal (investigational) study medication/intervention, whether related to the medicinal (investigational) study medication/intervention.

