11.3 Criteria for Adverse Events related to antibiotics

Adverse event ¹	Definition
Non-C. difficile associated diarrhea	> 3 loose stools per day associated with Antibiotic use, in absence of laxative or pre-existing enteritis (C. diff excluded from this category)
C. Difficile infection	Clinical signs and symptoms consistent with CDI and PCR test positive (and no laxatives)
Nausea/vomiting	Nausea and vomiting associated with antibiotic administration, in the absence of alternative explanation
Hematologic	Anemia: hemoglobin <10g/dL Leucopenia: WBC < 4500 cells/uL Thrombocytopenia: platelets <150x10 ³ /uL with levels below patient's baseline and in absence of bleeding or myelosuppressive therapy
Hepatobiliary	Cholestasis (bili > 51umol/L) or transaminitis (ALT, AST > 3x baseline) in the absence of existing hepatobiliary disease or recent biliary instrumentation
Renal	Increase in serum creatinine > 1.5x patient's baseline in the absence of precipitating factors such as intravenous contrast or other nephrotoxic agents, and not related to sepsis
Neurologic	Altered mental status, peripheral neuropathy, seizures in the absence of pre-existing neurological conditions or substance-related toxic events and unrelated to infectious syndrome
Dermatologic	Rash, including hives, non-hives rashes, red man syndrome – temporally associated with antibiotics; resolution with antibiotic cessation

Cardiac	QTc>440 ms in males or >460ms in females in absence of pre-existing arrhythmias, based on >2 ECGs
Anaphylaxis	Acute onset respiratory compromise, hypotension, or end organ dysfunction within minutes after antibiotic administration, without alternative explanations
Myositis	Increase in creatine kinase level >5 x patient's baseline, in absence of statin use or pre-existing myopathy

¹Adapted from Tamma et al, JAMA 2017

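### The DOOR ranks in section 12.2 are meant to be mutually exclusive, but Rank 1 sets the adverse-event bar at Grade IV while Ranks 2 to 4 give no grade, so Ranks 1 and 2 overlap

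*Protocol*

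**What the plan says.** The synopsis names DOOR with RADAR as the primary outcome at 28 days. Section 12.2 says the study will count each participant's DOOR events and "then assign a mutually exclusive rank". The adverse-event conditions in the rank table are:

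- Rank 1 (survivor, no failure-type event): "recurrence, complication AND NONE of Grade IV adverse event (AE"
- Rank 2 (survivor, no failure-type event): "recurrence, complication, AND at least one of AE"
- Rank 3: "Survival, at least one of treatment failure, persistence, recurrence, complication, AND NONE of AE"
- Rank 4: "Survival, at least one of treatment failure, persistence, recurrence, complication AND at least one AE"
- Rank 5: death, with no AE condition.

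Other sections bear on what AE means here. Section 12.1 describes the levels as "ranging from least desirable (death) to most desirable (e.g., cure, no adverse events", with no grade limit at the top. Section 11.1.1 defines the term without a grade: "An AE is any untoward medical occurrence in a participant". Section 11.3 lists the antibiotic-related events, for example "Anemia: hemoglobin <10g/dL", again without a grade but with exclusions attached to most rows. Section 11.3.2 grades every AE by CTCAE. The secondary objective in 3.2.2 and the planning rate in 12.6 both name Grade IV explicitly.

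**The concern.** Ranks 1 and 2 differ only in their AE condition, and the two conditions are not complements. Having no Grade IV event and having at least one AE of some grade can both be true of the same person. The adjudication panel then has no rule for that person, although the table is supposed to yield one rank each. For survivors with a failure-type event there is no overlap, but whether a lower-grade AE moves them from Rank 3 to Rank 4 depends on the same missing qualifier.

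The rank is part of the primary outcome, and 12.9 analyses the DOOR distribution, the DOOR probability and the component probabilities, including AE. If the threshold is settled only after data accrue, the primary endpoint is in part being defined with outcomes in view.

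**Working it through.** **1. Enumeration.** Take every combination of vital status (2), failure-type event yes/no (2) and worst AE none / Grade I-III / Grade IV (3). This gives 12 states. All six death states go to Rank 5 under any reading. The six survivor states are:

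| Failure-type event | Worst AE | Literal text | Grade IV in Ranks 1-4 | Any grade in Ranks 1-4 |
|---|---|---|---|---|
| No | None | 1 | 1 | 1 |
| No | I-III | **1 and 2** | 1 | 2 |
| No | IV | 2 | 2 | 2 |
| Yes | None | 3 | 3 | 3 |
| Yes | I-III | 4 | 3 | 4 |
| Yes | IV | 4 | 4 | 4 |

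On the literal text 11 of the 12 states get one rank and one gets two. Either uniform threshold repairs this, but the two repairs rank survivors with only Grade I-III events differently.

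**2. Illustrative size of the overlap.** Inputs:
- AE rate 12% within 30 days (12.4; hospitalized patients, grade not stated).
- Grade IV antibiotic AE rate 5-10%, excluding renal (12.6).
- Local ICU mortality 13% (12.6), standing in for 28-day death.
- Failure-type events in 10-20% of survivors (my assumption; the protocol gives no figure).

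Treating the 12% as all grades, the share q with only Grade I-III events is 12% - 10% = 2% to 12% - 5% = 7%, applied to survivors.

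Overlap share = (1 - mortality) × (1 - failure) × q

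- Low: 0.87 × 0.80 × 0.02 = 0.0139, or 17 of 1200.
- High: 0.87 × 0.90 × 0.07 = 0.0548, or 66 of 1200.

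With the 23% mortality that 12.4 quotes from a meta-analysis instead of 13%:

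- Low: 0.77 × 0.80 × 0.02 = 0.0123, or 15 of 1200.
- High: 0.77 × 0.90 × 0.07 = 0.0485, or 58 of 1200.

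The range is therefore roughly 1-6%.

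**3. Can the choice change the result?** Assume 13% death, 10% failure among survivors and 7.5% Grade IV AEs (the middle of 5-10%) in both arms. Let Grade I-III-only AEs be 20% in the intervention arm and 30% in the control arm. All of these are illustrative.

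- Grade IV reading: both arms have the distribution 0.724, 0.059, 0.080, 0.007, 0.130 over Ranks 1-5, so the DOOR probability is 50.0%.
- Any-grade reading: intervention 0.568, 0.215, 0.063, 0.024, 0.130; control 0.489, 0.294, 0.054, 0.033, 0.130. P(intervention better) + ½ P(tie) = 0.350 + ½ × 0.362 = 0.531.

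With the two arms' Grade I-III rates exchanged, symmetry gives 1 - 0.531 = 0.469. The same data can read as no difference, benefit or harm, depending on the threshold and on where the lower-grade events fall.

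**4. Sample sizes.** With (z₀.₉₅ + z₀.₈₀)² = 6.183:

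- H1: 2 × 6.183 × 8² / 1.5² = 351.7, so 352 per group, as stated.
- H2: 6.183 × (0.18 × 0.82 + 0.20 × 0.80) / (0.04 + 0.02)² = 528.3, so 529 per group, as stated.

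Neither formula uses the rank definition.

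**The case against.** The best defence is that the abbreviation in Rank 1 follows directly on Grade IV adverse event, so AE in the rows below could be shorthand for Grade IV. The paired none / at-least-one pattern, the Grade IV secondary objective and the Grade IV planning rate all fit that, and the overlap then vanishes. This may well be what was meant. But no sentence says so. AE is already defined without a grade in 11.1.1. Section 12.2 itself uses it ungraded just before the table, and 12.1 puts no adverse events at the top level. The 12.1 wording is only an example in a general description, so it does not settle the matter, but it points the other way.

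A second defence is that DOOR counts only antibiotic-related events, so the broad 11.1.1 definition is not the operative one. That is fair as to type of event. It does not supply a grade, because the 11.3 criteria carry none.

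Several stronger readings are tempting and should be resisted.

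- **The 2-7% as a lower bound.** It subtracts rates from different populations and definitions, and only failure-free survivors can overlap.
- **Comparison with the 4-point margin.** That margin is a between-arm limit for H2. It does not measure misclassification on DOOR.
- **The all-cause kidney-injury rate of 26-67% in 12.6 as a guide to size.** The renal criterion in 11.3 excludes sepsis-related cases and those with other precipitants. The haematologic and cardiac rows carry exclusions too, so it is not shown that the AE ranks would mostly reflect ICU illness.
- **Dilution towards 50%.** Counting lower grades could equally create separation, as step 3 of the working shows.

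**Conclusion.** The point holds as an internal contradiction in the definition of the primary outcome. The ranks are required to be exclusive, and on the literal text one of 12 outcome states satisfies both Rank 1 and Rank 2. The overlap is confined to those two ranks; between Ranks 3 and 4 the threshold is ambiguous but nothing is double-classified. The protocol's own signals conflict: 12.1 and 11.1.1 point to any grade, Rank 1 and the secondary objective to Grade IV. Because the protocol states the table and claims exclusivity for it, this is an error in stated text and not detail left to an analysis plan.

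The size is uncertain. Roughly 1-6% of participants rests on treating the 12% as all-grade, the 5-10% as its Grade IV part, and an assumed 10-20% failure rate. The direction of any effect on the DOOR probability is not determined. A reader might infer that the sample size is undermined, but both stated figures reproduce and neither depends on this point.

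**What to change.** Before the first interim analysis (planned at one third of enrolment), state one AE threshold in identical words in Ranks 1 to 4. The choice most consistent with Rank 1 and the secondary objective is a Grade IV antibiotic-related AE meeting the 11.3 criteria, CTCAE-graded and adjudicated by the blinded panel: none for Ranks 1 and 3, at least one for Ranks 2 and 4. Amend the top-level description in 12.1 to match, add a sentence to 11.3 saying that only Grade IV events enter DOOR, and report lower grades descriptively.

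Any grade throughout would also restore exclusivity, but it ranks patients differently and would mean rewriting Rank 1, so the sponsor should make the choice explicitly.

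The cost is a few words per row, a sentence in 11.3 and an edit to 12.1, with no change to the sample size. The downside of the Grade IV choice is that Grade I to III events no longer influence the rank.
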